assessments must view and rate nine videos of standard interviews of actors depicting delirious and non-delirious patients. This process will help to demonstrate the success of the training process and the extent to which researchers reproducibly score the CAM. To establish the reliability of delirium assessments in the clinical setting, trained members of the research team will separately assess 30 patients not enrolled in the ENGAGES study at similar time points (e.g., within two hours of each other). These assessments will determine the test-retest reliability of delirium assessments by the research team. This approach will provide > 90% power to demonstrate a Kappa statistic of >0.6, representing substantial or greater agreement between raters.⁹⁶

A structured process will be implemented to assess and ensure the quality of the delirium assessments. Every delirium assessment will be reviewed within three days with a fellow member of the research team to assess internal consistency of scoring and completeness. On a weekly basis, investigators at Washington University will review all the delirium assessments, will address methodological inconsistencies, and will attempt to resolve controversies. Monthly, there will be a teleconference including investigators from Hebrew SeniorLife/Harvard University and from Washington University to review challenging delirium assessments and to ensure that the rigor of assessments remains appropriate. During these conferences, the need for focused and comprehensive refresher training in delirium assessment⁹⁵ will be determined.

If participants agree, these assessments may be videotaped for training and education of the research team. The videotapes will include the patients face.

ii) Health-related Quality of Life (Aims 2 and 3 in Figure 2)

As part of the ongoing SATISFY-SOS study, patient self-reported Health-related Quality of Life information will be assessed through the Veteran's RAND 12-item Health Survey at baseline (preoperatively) and during follow-up (30-day and 1-year). The VR-12 was derived from the Veterans RAND 36 Item Health Survey (VR-36) and contains 12 items relating to quality of life, including physical and mental health, as well as specific questions about functional status. Physical and Mental Health Summary Scores will be calculated. The VR-12 has been validated and is widely applied as a metric for tracking health-related quality of life in the United States.⁹⁷

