We will follow the intention-to-treat principle for all analyses. The primary endpoint of our analysis is the incidence of postoperative delirium as defined previously. The incidence of delirium will be compared between groups using a chi-square test, and the difference in delirium incidence with 95% confidence intervals will be calculated. Prespecified exploratory subgroup analyses: we will test for effect modification by known baseline delirium risk factors (i.e., age [<70 and ≥ 70], sex, history of falls, and type of surgery [cardiac versus non-cardiac]).

ii) Effectiveness of EEG-guided anesthesia protocol in improving patient reported outcomes of health-related quality of life and preventing postoperative falls (Aim 2 in Figure 2)

Health-related quality of life

Random effects regression models based on PROC MIXED in SAS will be used to compare Physical Summary Score change over 12 months between the intervention and usual care group by introducing terms for time, indicator variables for treatment group and time x treatment group interactions with the latter set of regression coefficients of primary interest. The model will be controlled for baseline health-related quality of life. Potential confounding factors including age, gender and relevant comorbidities will be evaluated and controlled for in the model. We will utilize the same analysis approach to evaluate the Mental Summary Scores.

The analysis is primarily based on the following model: $Y_{it} = \alpha + \beta_1 t + \beta_{2A} X_{i1} + \beta_{3A} X_{i1}t + \beta_4 Y_{i0} + e_{it}$ (1) where Y_{it} = QOL for subject i at time t , where $t = 0$ for baseline, $t = 1$ for 12 months. $X_{i1} = 1$ if i th subject is in the Intervention group, = 0 otherwise $e_{it} \sim N(0, \sigma^2)$ β_{3A} is the mean difference in Physical Summary Score change between the Intervention and usual care groups. The coefficient β_{2A} allows for mean differences in Physical Summary Scores between groups at baseline. The coefficient β_4 allows the change in Physical Summary Score to depend on initial level.

Postoperative falls

Chi square test will be used to compare the incidence of falls at 12-months postoperatively between patients in the EEG-guided and in the usual care groups.

iii) Explore whether a multi-component safety intervention is associated with improved patient reported health-related quality of life and decreased incidence of postoperative falls (Aim 3 in Figure 2)

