Our sample size calculations are based on the anticipated delirium incidence and effect size for our primary endpoint analysis. Based on results of a previously published meta-analysis of four studies investigating the use of BIS-guided anesthetic administration, we conservatively assume an incidence of postoperative delirium in the routine anesthesia care group of 25%.²⁹ We performed a sample size sensitivity analysis and calculated different scenarios with different values for the delirium incidence in the intervention arm and corresponding power (80%, 90%, and 95%). With a two sided alpha $<5\%$ and 1,232 patients (616 per arm), the trial will have $>95\%$ power to detect an absolute decrease in delirium incidence $\geq 9\%$, $>90\%$ power to detect a decrease in delirium incidence $\geq 8\%$, and $>80\%$ power to detect a decrease in delirium incidence $\geq 7\%$. With a 7% decrease in delirium incidence, the 95% confidence interval would be approximately 3% to 12%. Even a 3% decrease in delirium incidence would be clinically important, suggesting that delirium would be prevented in one out of every 33 at risk patients who received EEG-guidance of general anesthesia.

ii) Health Related Quality of Life

The overall sample size of our study is defined through estimations of the primary outcome (delirium). For secondary analyses, we assume that ~80% of our trial population (~1,000 participants) will have completed the trial and the 1-year follow-up survey. With this sample size of 1,000, we can detect a difference of 0.5 points (standard deviation of 2.5) in the mean change of Physical Health Score from baseline to 1 year between the intervention and usual care group with a power of $>80\%$ and a two-sided alpha level of $p<0.05$.

iii) Postoperative Falls

This calculation is similarly based on the assumption that ~80% of our trial population (~1,000 participants) will have completed the trial and the 1-year follow-up survey. Based on a study that showed a preoperative fall prevalence of 33% over six months preoperatively in a similar patient population to the ENGAGES trial, we will conservatively assume an incidence of postoperative falls at 1-year in the routine anesthesia care group of 40%.¹¹⁰ With a sample size of 1,000, we will have $>80\%$ power to detect an absolute risk reduction of 12% between the EEG-guided and the usual care group at a two-sided alpha level of $p<0.05$.

Analysis of Pragmatic Elements of the ENGAGES Study

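### In the planning 95% CI for a 7-point fall in delirium, the lower limit printed as 3% works out at 2.4%, just under the decrease that the protocol calls clinically important

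*Combined protocol and SAP*

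**What the plan says.** All the relevant figures stand in one paragraph of the Combined protocol and SAP (Sample Size Calculations, i) Decrease in Delirium).

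- Control rate: it assumes "an incidence of postoperative delirium in the routine anesthesia care group of 25" percent.
- Size and power: with "1,232 patients (616 per arm), the trial will have" more than 95%, 90% and 80% power for decreases of at least 9, 8 and 7 points respectively, at a two-sided 5% level.
- Planned precision: "With a 7% decrease in delirium incidence, the 95% confidence interval would be approximately 3% to 12" percent.
- Interpretation: "Even a 3% decrease in delirium incidence would be clinically important", which the protocol equates to one case prevented in every 33 patients.

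Statistical Analyses, i) names the quantity that the trial will report: after a chi-square test, "the difference in delirium incidence with 95% confidence intervals will be calculated". Randomization and Blinding gives 1:1 allocation. The intervention-arm rate of 18%, the event counts and the interval method are not written out. The separate one-year analysis plan deals with mortality, quality of life and falls, and does not restate this interval.

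**The concern.** A large-sample interval for a difference in proportions should be centred on, or very near, the difference itself. The printed limits have their midpoint at (3 + 12)/2 = 7.5 points, while the stated decrease is 7. One of the limits therefore looks wrong.

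The lower limit is the one that readers will use. It is followed at once by the statement that a 3% decrease would matter clinically. Taken together, the two sentences suggest that an observed 7-point fall would exclude any effect smaller than the important one. If the true lower limit is below 3%, the paragraph slightly overstates the planned precision at the value it singles out.

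**Working it through.** **Inputs.** Control rate p1 = 0.25, n = 616 per arm and difference d = 0.07, all from Sample Size Calculations, i). Hence p2 = 0.25 − 0.07 = 0.18. Allocation is 1:1. The confidence level is 95%, so z = 1.96.

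**Step 1. Are the inputs read as the protocol uses them?** The power of the two-sided 5% comparison of proportions with 616 per arm and 25% in the control arm is:

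| Decrease | Computed power | Stated |
|---|---|---|
| 7 points | 84.9% | >80% |
| 8 points | 93.2% | >90% |
| 9 points | 97.5% | >95% |

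All three statements hold, so the inputs are read correctly.

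**Step 2. The interval.**

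- Standard error = √[(p1(1 − p1) + p2(1 − p2))/n] = √[(0.1875 + 0.1476)/616] = √(0.3351/616) = 0.02332
- Half-width = 1.96 × 0.02332 = 0.0457, or 4.57 points
- 95% CI = 7 ± 4.57 = **2.43% to 11.57%**

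**Step 3. Does another standard method give 3%?**

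| Method (25% vs 18%, 616 per arm) | 95% CI |
|---|---|
| Unpooled Wald | 2.43 to 11.57 |
| Pooled standard error | 2.41 to 11.59 |
| Newcombe (Wilson score) | 2.41 to 11.56 |
| Agresti-Caffo | 2.41 to 11.55 |
| Wald with continuity correction | 2.27 to 11.73 |

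Each rounds to 2% to 12%. A 90% interval, 3.16 to 10.84, does not match the printed figures either.

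**Step 4. What would give the printed limits?** A 7.5-point fall (25% vs 17.5%) gives 2.95 to 12.05. The printed width (9 points) is close to the computed one (2 × 4.57 = 9.14), so the discrepancy is mainly one of position. The documents do not show how it arose.

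**Step 5. Whole patients.** A quarter of 616 is 154 events, and 18% of 616 is 110.88.

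- 154 vs 111 (6.98 points): 2.41 to 11.55
- 154 vs 110 (7.14 points): 2.58 to 11.71

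**Step 6. Size in the protocol's own terms.** The lower limit is 3 − 2.43 = 0.57 points too high. As a number needed to treat, it is 1/0.0243 ≈ 41 rather than 1/0.03 ≈ 33.

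**The case against.** The best defence is that the figure is labelled approximate, is given in whole points and rests on no stated event count. With 154 control events, six intervention-arm counts (108 to 113) would display as 18% and as a 7-point fall. Three of them (108, 109 and 110) give intervals that round to 3% and 12%: 2.92 to 12.02, 2.75 to 11.86 and 2.58 to 11.71. Equally, a lower limit that merely rounds to 3% needs only 2.5%. At 25% vs 18% that takes (1.96/0.045)² × 0.3351 ≈ 636 per arm, just 20 more than planned.

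Much of this stands. It shows that the slip is of rounding size, with no wrong method or input behind it. It does not rescue the sentence as printed. The count nearest to 18% is 111, which rounds to 2%. The three favourable counts all correspond to falls larger than the stated 7 points, and even they leave the unrounded lower limit below 3%.

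The defence can add that the protocol never requires the lower limit to exceed 3%. Its closing remarks under Statistical Analyses tie implementation to statistical significance and to the estimated effect size. That is also correct, and it limits the consequence to interpretation.

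**Conclusion.** The point holds for one limit. At the protocol's own inputs the interval is about 2.4% to 11.6%. The printed upper limit is right after rounding, and the printed lower limit is about 0.6 points too high and falls on the other side of the 3% named in the next sentence. This is a minor error.

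The result assumes exactly 25% vs 18% and that all 616 patients per arm contribute, as the delirium calculation does. It does not depend on the choice among the usual 95% methods.

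Three stronger readings may tempt a reader, and the documents support none of them.

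- *The whole interval is wrong.* It is not, since 11.6% rounds to 12%.
- *The trial is too small to establish a clinically important effect.* The sample size was set by power, the power statements reproduce, and no rule compares the lower limit with 3%.
- *The reliability statement under Outcome Measures, i) contains a similar error.* It says: "This approach will provide > 90% power to demonstrate a Kappa statistic of >0.6, representing substantial or greater agreement between raters". The surviving text does not give the inputs to that calculation, text is lost nearby, and more than 90% power is attainable under some assumptions about raters and true agreement. No error can be shown there.

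**What to change.** Replace the sentence with wording such as: *For a 7-point fall in delirium (25% versus 18%, 616 per arm), the 95% confidence interval for the difference would be about 2.4% to 11.6%.* If whole points are preferred, print 2% to 12%. Name the interval method in the same place, so that the figure can be reproduced. The remark that a 3% decrease would be clinically important can stay, because it does not depend on the interval.

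The cost is a change of wording. The 1,232 patients, the chi-square test, the stated powers for 7, 8 and 9 points and the plan to report the observed interval all stay as they are.

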### ***Hypothesis 2: Is EEG Guidance Intervention Associated with Improved Quality of Life One Year After Surgery?***

*Patient Population:* Patients randomized to intervention or control (N = 1232)

*Primary Predictor Variable:* EEG guidance intervention

(X=0 for control or X=1 for intervention)

Intention to treat

*Outcomes:* Veterans RAND 12-Item Health Survey (VR-12) physical component score (PCS), VR-12 mental component score (MCS), one year postoperatively

- Partially completed VR-12 surveys will not be scored and will be considered missing.

*Data Description Plan:* Box plots of VR-12 PCS and MCS at baseline, 30 days, and 1 year for the two groups. Provide median, interquartile range, and range at each time point.

*Analysis Plan:* Generalized linear model

$$y_{365} = \beta_0 + f(y_0) + \beta_1 x + \beta Z + \varepsilon$$

- In this equation,  $y_{365}$  is the quality of life (either VR-12 PCS or VR-12 MCS) at one year, and  $y_0$  is the quality of life metric at baseline.  $x$  is the EEG guidance intervention ( $x=0$  for control or  $x=1$  for intervention).  $Z$  is a vector of additional variables for which we will adjust.
- $f(y_0)$  is a potentially nonlinear function describing the relationship between baseline quality of life and quality of life at one year. This function will be modeled using splines.
- Will perform unadjusted ( $Z = \text{null}$ ) and adjusted ( $Z$  not null) analyses. Will adjust for age, sex, American Society of Anesthesiologists (ASA) physical status classification (1-2 vs 3 vs 4-5), number of comorbid conditions, baseline poor functional capacity (<4 METS), history of falls (yes/no within previous 6 months), evidence of abnormal cognition (preoperative Short Blessed Test score > 4), surgery type (cardiac versus non-cardiac), length of anesthesia (Anesthesia Stop – Anesthesia Start)
  - o Multiple imputation may be performed to address missing values of these variables
- Any patient with missing quality of life either at baseline or at one year will be excluded.
- $H_0: \beta_1 = 0$  (The null hypothesis is that the EEG guidance intervention has no association with postoperative quality of life.)

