Randomization will be performed at the patient level using computer-generated assignment. Eligible patients who provided written informed consent will be randomized to receive the intraoperative electroencephalography-guided protocol or routine care. In order to ensure that there is not major imbalance between group assignments with respect to history of falls and cardiac surgery, subjects will be randomized (1:1) between the EEG-guided and routine care groups in blocks of 20 within these four strata (i.e., cardiac surgery with a history of falls within 6 months, cardiac surgery without a history of falls within 6 months, non-cardiac surgery with a history of falls within 6 months; and non-cardiac surgery without a history of falls within 6 months). Trained members of the research team will enroll participants and will implement the assignment of participants to the EEG-guided or usual care protocols. Group assignment will be revealed to members of the anesthetic team only when the patient enters the operating room by opening a sequentially numbered, opaque, sealed envelope in a sequence generated by one of the study's data analysts. Patients and their families will be blinded to group allocation and different members of the research team will assist with the intervention in the operating room (will not be blinded to the intervention) from those conducting the postoperative assessments (will be blinded to the intervention).^{51,52} To reduce predictability of a random sequence, details of patients already randomized and prior group assignments will be recorded in a separate document that is unavailable to those who enroll participants and assign interventions.

Primary Intervention – EEG-guided Anesthetic Protocol

The primary intervention to which patients will be randomized in this study is a pragmatic EEG-guided anesthetic protocol (See Appendix). All anesthesia practitioners will receive a targeted educational session on recognition of EEG patterns typically occurring during general anesthesia. The content will be similar to that described in an article where we demonstrated that anesthesiologists could estimate BIS (processed EEG

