The following limitations should be considered. A single clinical trial should seldom be regarded as definitive. As there is no clear estimate for the prior probability that EEG guidance of anesthesia prevents postoperative delirium, if the results of this trial do suggest that EEG-guidance of anesthesia might decrease delirium at the arbitrary statistical threshold of $p < 0.05$, it will be necessary to replicate this finding in future studies. On the other hand, even if the study finds a non-significant (at the arbitrary threshold of $p > 0.05$) decrease in delirium in the EEG-guided group, it is likely that follow-up studies will be warranted to clarify whether or not there is a clinically meaningful reduction in delirium with EEG-guidance of anesthesia, and whether there are specific patient populations that might especially benefit from this intervention. If EEG-guidance of anesthesia can prevent postoperative delirium, demonstrating its effectiveness will depend on clinicians' adherence to the protocol. However, the inability to blind clinicians to the trial allocation group is a potential source of bias and confounding. We are attempting to confirm that clinicians do alter anesthetic management based on the intervention during the pilot phase of the study. The inclusion of patients in a clinical trial focused on the prevention of delirium, and the provision of practical educational information to patients and family members could decrease the incidence of postoperative delirium. Furthermore, if the multi-component intervention is successful in preventing falls and in improving quality of life, this could curtail our ability to detect an impact of the EEG-guided anesthetic protocol on these outcomes. In addition to the pragmatic structured chart review, there are two clinical assessment methods that will be used to diagnose delirium: the CAM-ICU and the CAM. The CAM-ICU is less sensitive than the CAM, but is the only instrument that has been validated for patients who are non-verbal (i.e., with a breathing tube or tracheostomy in place). Based on our institutional data, the vast majority of patients enrolled in the study will be extubated within the first two postoperative days. Therefore, most patients will have delirium assessments with the CAM, which is the more sensitive and specific instrument. We will also test whether intubation status modifies the result in secondary analysis. The study design includes a 30-day and a 1-year follow up for patient reported outcomes, and incomplete follow-up is therefore a potential limitation. Based on our previous B-Unaware and BAG-RECALL studies,^{40,41} we are confident that we can achieve a 30-day follow up rate of >90%. In our SATISFY-SOS cohort, the 1-year follow up has yielded approximately 66% response rate. We have performed sensitivity analysis in our power calculations and have taken into account this potential attrition in our methods. Furthermore, we plan to enhance follow-up by using supplementary phone calls from members of the study team. As delirium is a fluctuating disorder, there is a risk that it can be missed by periodic assessments. We are attempting to mitigate this by assessing patients for delirium during a time of day (afternoon/evening) when delirium occurs more commonly. Furthermore, we are incorporating structured chart review, which has been validated as a complementary approach that increases the detection of delirium.^{93,94}

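### The SAP discards every answered item on a partly completed VR-12 and then assigns extreme scores; impute the skipped items instead, and show the 66% response scenario beside the quality-of-life power

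*Combined protocol and SAP*

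**What the plan says.** **Scoring and exclusion.** SAP Hypothesis 2, under Outcomes, states: "Partially completed VR-12 surveys will not be scored and will be considered missing". Its analysis plan leaves out any patient lacking quality of life at baseline or at one year. Multiple imputation is permitted there, but only for the adjustment covariates.

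**Bounding analyses.** In Hypothesis 2, Planned Sensitivity Analyses 1 and 2, a missing baseline score becomes the stratum mean. A missing one-year score becomes the stratum maximum in one arm and the stratum minimum in the other, with the arms swapped between the two analyses. Strata are surgery type by falls history, and patients who died are excluded. Because a partial form counts as missing, these rules apply to it.

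**Power.** The protocol's Sample Size Calculations, part ii, says "we assume that ~80% of our trial population (~1,000 participants) will have completed the trial and the 1-year follow-up survey" and, on that number, "we can detect a difference of 0.5 points (standard deviation of 2.5) in the mean change of Physical Health Score" with power above 80% at two-sided 0.05. No other response rate is shown for this outcome. Strengths and Limitations says "In our SATISFY-SOS cohort, the 1-year follow up has yielded approximately 66% response rate", then "We have performed sensitivity analysis in our power calculations and have taken into account this potential attrition in our methods", and adds that extra phone calls are planned.

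**The concern.** A patient who answers 11 of 12 items at one year is handled like one who returned nothing. The main analysis loses that patient. The two bounding analyses replace 11 real answers with the most extreme score seen in the stratum. Those analyses are meant to show how far unknown outcomes could move the result; here part of the movement comes from outcomes that are largely known. A robust result could look fragile for that reason.

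The same rule bears on power. The protocol counts people who complete the survey, whereas the SAP analyses people with two fully completed forms. The protocol makes no allowance for the difference, and its only empirical one-year response rate is well below the rate used for power.

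**Working it through.** **1. Reproduce the stated power.** Inputs from Sample Size Calculations ii: difference 0.5, SD 2.5, total N 1,000, two-sided 0.05. Equal arms follow from the 1:1 allocation in Randomization and Blinding.

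Noncentrality = 0.5 / (2.5 × √(4/N)). At N = 1,000 this is 0.5 / 0.158 = 3.16, and a two-sample t test has 88.5% power. The claim of more than 80% reproduces. An exact 80% of 1,232 is 986, with power 88.0%.

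**2. Put in the protocol's own response figure.** 0.66 × 1,232 = 813. Noncentrality = 0.5 / 0.175 = 2.85, power 81.3%. The claim still holds.

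**3. Find the margin.** The smallest total N giving 80% is 787 (80.01%); 786 gives 79.96%. So 813 − 787 = 26 responders, or 26/813 = 3.2%, can be lost to partial forms and missing baselines combined. The documents give no such rate. Assumed losses from 813:

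| Loss (assumed) | N scored | Power, unadjusted |
|---|---|---|
| 2% | 797 | 80.5% |
| 3% | 789 | 80.1% |
| 5% | 772 | about 79% |
| 10% | 732 | 77.1% |

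**4. Allow for baseline adjustment.** The protocol and SAP models both condition on baseline. If 2.5 is the SD of raw change and the variance is equal at both times (both assumptions), adjustment multiplies the variance by (1 + r)/2, where r is the baseline to one-year correlation. The N needed for 80% is then 591 at r = 0.5 and 748 at r = 0.9. The documents do not give r.

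**5. Precision lost by the scoring rule.** Dropping a share p of otherwise usable patients multiplies the standard error by 1/√(1 − p): 1.026 at p = 5% and 1.054 at 10%. Imputation would recover part of this.

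**6. Widening of the bounds.** Let p be the share of living patients in each arm with a partial one-year form, and R the stratum maximum minus minimum, averaged over strata. In the best-likely case these patients add about p × max to the intervention mean and p × min to the control mean, a shift of about pR in the difference. The worst-likely case shifts it by −pR, so the gap between the bounds widens by about 2pR.

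Neither p nor R is given. The range at which the shift reaches the protocol's 0.5-point planning difference is R = 0.5/p: 25 points at p = 2%, 10 at 5% and 5 at 10% (shares assumed).

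**The case against.** **The scoring rule is prespecified, identical in both arms, and the bounds are meant to be extreme.** This is true, and nothing in the documents shows that the rule biases the treatment comparison. One might infer that it selects against frailer patients who skip items, but the documents offer no support for that. The cost to information and to the bounds remains: a bounding analysis need not treat recorded answers as unknown.

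**The partial-form rate may be negligible.** It may be, and then the gain is small. The documents do not say.

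**A reader might infer that the power claim is false, or that it survives only with 787 scored patients.** The documents do not support either reading. The claim holds at 1,000 and at 813. The 787 applies to an unadjusted comparison of change scores, while both planned models adjust for baseline and may need fewer patients. The 66% is an approximate rate from the wider SATISFY-SOS cohort, not an ENGAGES rate after extra calls. A claim that stays true at 66% is also compatible with the protocol's statement that attrition was considered; the calculation is simply not shown. The unadjusted shortfalls in the table rest on assumed losses and are small.

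**Restating power changes little.** Delirium sets the sample size and the SAP fixes N at 1,232. That stands, and it is why the power point is one of reporting only.

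**Conclusion.** The scoring rule should be improved. It throws away observed VR-12 answers, removes those patients from the main analysis, and widens the best- and worst-likely bounds by about pR on each side. The size cannot be fixed from the documents, because p and R are not given. The pR figure assumes equal partial-form shares and a similar stratum mix in the two arms.

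The power statement is correct as it stands and thinly supported: 81.3% at 66% response, with room to lose 26 of 813 before an unadjusted test drops below 80%. This rests on an SD of 2.5, for which the section gives no source. Baseline adjustment and the extra phone calls could each widen the margin. What is missing is the 66% scenario that the limitations section implies was examined.

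**What to change.** **SAP Hypothesis 2.** Add item-level multiple imputation for partly completed baseline and one-year VR-12 forms, using the patient's answered items, the adjustment covariates and the arm. Score each completed form, fit the planned model in each imputed set and pool. This must be written as a new step, because the imputation now allowed covers only covariates. Keep complete forms only as a sensitivity analysis.

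Restrict the maximum and minimum rules to living patients who returned no one-year VR-12 items, and the stratum-mean rule to those with no baseline items. Score the matched SATISFY-SOS patients the same way in Sensitivity Analysis 3. Report the number of partial forms by arm and time point.

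**Protocol.** In Sample Size Calculations ii, show power at 813 and with a stated allowance for unscored forms, and give the source of the SD. SATISFY-SOS collects VR-12 at both time points and could supply it. Bring the attrition sentence in Strengths and Limitations into line.

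**Cost.** Extra imputation code, a missing-at-random assumption for skipped items, and a less generous displayed power. No more patients and no new data collection.
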